9.4 Safety Assessments

Safety will be evaluated for all treated patients using NCI CTCAE v4.03.²⁹ Safety assessments will be based on medical review of both solicited and spontaneously reported AEs, SAEs, and MEOIs including symptoms, physical examination findings, vital signs, laboratory findings, ECGs, and discontinuations for AEs. After initiation of study drug, all AEs, regardless of relationship to study drug, will be reported until 30 days after the last dose of study drug or until initiation of another anti-cancer therapy, whichever occurs first.

9.4.1 Definitions

Adverse Event (AE) - Any untoward medical occurrence in a patient or clinical investigation patient administered a pharmaceutical product, medical treatment, or procedure and which does not necessarily have to have a causal relationship with this regimen. An AE can therefore be any unfavorable and unintended sign (including an abnormal laboratory finding, for example), symptom, or disease temporally associated with the use of a medicinal product, medical treatment, or procedure whether or not considered possibly, probably, or definitely related to the medicinal product.

Unexpected Adverse Event – An AE is “unexpected” when its nature (specificity), severity, or frequency are not consistent with the known or foreseeable risk of AE associated with the research procedures described in the protocol, informed consent form, or the Investigator Brochure.

Serious Adverse Event (SAE) – Any adverse event occurring that results in any of the following outcomes:

- Death
- A life-threatening AE
- Inpatient hospitalization or prolongation of existing hospitalization
Note: Hospitalizations not to be reported as SAEs include admissions for a planned medical/surgical procedure (such as scheduled tumor excision or debulking surgery) or routine health assessment requiring admission for baseline/trending of health status documentation (e.g., routine colonoscopy) or admission for social purposes such as lack of housing, economic inadequacy, care-giver respite, or family circumstances.
- A persistent or significant disability/incapacity
- Results in a congenital anomaly/birth defect
- Is a medically important condition which is judged by a health care professional as serious

The term “life-threatening” refers to an event in which the patient was at risk of death at the time of the event, and it does not refer to an event that hypothetically might have caused death if it were more severe.

Disability refers to a substantial disruption of a person’s ability to conduct normal life function.

Medical and scientific judgment will be exercised in deciding whether expedited reporting is appropriate in other situations, such as important medical events that may not be immediately life-threatening or result in death or hospitalization but may jeopardize the patient or may require intervention to prevent one of the outcomes listed in the definition above. These may also be considered serious. Examples of such events are intensive treatment in an emergency room or at home for allergic bronchospasm; or blood dyscrasias or convulsions that do not result in hospitalization.

When there is doubt regarding an AE meeting the criteria for an SAE, the Investigator should default to reporting the AE as an SAE.

Pregnancy – Although pregnancy is not considered an SAE, and is instead a normal human experience, all pregnancies reported in the month before or after the last investigational injection

must be reported to the Sponsor using the Pregnancy Report Form as outlined in the Site Safety Manual.

Overdose– An overdose is defined as the accidental or intentional administration of any dose of a product that is considered both excessive and medically important. In this trial, an overdose will be defined as ≥ 1000 mg (5x the dose) of atezolizumab. For reporting purposes, an overdose will be considered, regardless of adverse outcome, as an important medical event. All cases of overdose must be reported immediately to the Sponsor.

Medical Events of Interest – Select non-serious AEs and SAEs identified by the Sponsor will be considered MEOIs. All MEOIs outlined in [Section 9.4.8](#) must be reported to the Sponsor using the MEOI Report Form as outline in the Site Safety Manual.

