5.3 Rationale for Dose Selection

The doses of the CMB305 components chosen for this study are the following: 1×10^{10} vg of LV305, 250 μ g NY-ESO-1, and 5 μ g GLA-SE. These doses were chosen based on separate Phase 1 studies of each agent (Protocols ID-LV305-2013-001 and IDC-G305-2013-001) and

available safety and immunogenicity data which demonstrated that the CMB305 components were safe and effective in boosting the immune response against NY-ESO-1 and achieving SD and/or PFS.^{10,11} Furthermore, the first in-human trial of CMB305 is currently being conducted (Protocol IMDZ-C131) using the same doses chosen for this study. The use of LV305 and CMB305 is also being investigated in combination with anti-PD-1 agents in these Phase 1 studies. At the time of this protocol, no DLTs or treatment-related SAEs have been reported in over 4 dozen patients treated in these clinical studies.

Atezolizumab will be dosed according to available PK data from previous clinical studies. Preliminary PK data of 0.03-20 mg/kg atezolizumab appeared to show linear PK at doses ≥ 1 mg/kg. For the 1 mg/kg and 20 mg/kg dose groups, the mean apparent clearance (C_L) and mean volume of distribution at steady state (V_{ss}) had a range of 3.11 to 4.14 mL/kg and 48.1 to 67.0 mL/kg, respectively, which was consistent with the expected profile of an IgG1 antibody in humans. The fixed dose of 1200 mg (equivalent to an average body weight-based dose of 15 mg/kg) was selected on the bases of both non-clinical studies and available clinical activity, safety, PK, and immunogenicity data developed by Roche. Anti-tumor activity has been observed across doses from 1 mg/kg to 20 mg/kg administered every 3 weeks. The maximum tolerated dose (MTD) of atezolizumab was not reached and no DLTs have been observed at any dose in the PK study.

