7.1.3.1 Investigational Drug Packaging and Labeling

The atezolizumab drug product is provided in a single-use, 20-mL glass vial as a colorless-to-slightly-yellow, sterile, preservative-free clear liquid solution intended for IV administration. The vial is designed to deliver 20 mL (1200 mg) of atezolizumab solution but may contain more than the stated volume to enable delivery of the entire 20 mL volume. The atezolizumab drug product is formulated as 60 mg/mL atezolizumab in 20 mM histidine acetate, 120 mM sucrose, 0.04% polysorbate 20, pH 5.8.

For further details, see the atezolizumab Pharmacy Manual and IB.

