7.1.3.3 Dose Preparation for Administration to the Patient

Administration of atezolizumab will be performed in a setting with emergency medical facilities and staff who are trained to monitor for and respond to medical emergencies. A dose of 1200 mg atezolizumab will be administered by IV infusion every 3 weeks. The investigational products will be delivered in infusion bags with IV infusion lines with product contacting surfaces of polyvinylchloride (PVC) and polyolefin and 0.2 µm in-line filters (filter membrane of polyethersulfone). No incompatibilities have been observed between atezolizumab and PVC or polyolefin infusion materials (bags and infusion lines).

Specific instructions for the preparation and administration of the atezolizumab infusion solution are contained within the Pharmacy Manual.

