7.2.2 Dose Modification Guidelines

Dosing interruptions are permitted in case of medical/surgical events or logistical reasons not related to study therapy (e.g., elective surgery, unrelated medical events, patient vacation, and/or holidays). Patients should be placed back on study therapy within 3 weeks of scheduled interruption, unless otherwise discussed with Sponsor. The reason for interruption should be documented in the patient's study records.

There are no adjustments for dose delay for a given patient, and treatment delays for the CMB305 components that are >14 days from the treatment plan before Visit 12 will not be allowed. During the study, if a patient experiences a DLT, treatment of that patient will be suspended. A patient may be considered for receiving further injections of the LV305, G305, or atezolizumab investigational drug product on a case-by-case basis following evaluation of the benefit/risk ratio to the patient by the Investigator and Medical Monitor, in consultation with the

independent DMC (e.g., for patients who have experienced a tumor response and had a non-life- and non-organ-threatening DLT, continuation of treatment as per protocol may be considered).

No reduction or modification of the atezolizumab dose will be allowed. Any toxicities associated or possibly associated with atezolizumab treatment should be managed according to standard medical practice. Additional tests, such as autoimmune serology or biopsies, may be used to determine a possible immunogenic etiology. As a result, study treatment must be withheld for AEs or infusions reactions associated with atezolizumab treatment as outlined in [Appendix F](#).

While most irAEs observed with immunomodulatory agents have been mild and self-limiting, such events should be recognized early and treated promptly to avoid potential major complications. The primary approach to Grade 1-2 irAEs is supportive and symptomatic care; for higher grade irAEs, steroids by mouth or parenterally are given, and either skipping a dose or stopping therapy is appropriate. Recurrent Grade 2 irAEs may also mandate skipping a dose of atezolizumab or the use of steroids as outlined in [Appendix F](#).

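### The atezolizumab overdose definition contradicts itself: 1000 mg is 0.83 times the fixed 1200 mg dose, and five times that dose is 6000 mg

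*Protocol*

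**What the plan says.** Protocol Section 9.4.1 opens with a general definition: "An overdose is defined as the accidental or intentional administration of any dose of a product that is considered both excessive and medically important". It then sets the trial-specific threshold: "In this trial, an overdose will be defined as ≥ 1000 mg (5x the dose) of atezolizumab". Two consequences follow in the same paragraph: "For reporting purposes, an overdose will be considered, regardless of adverse outcome, as an important medical event", and "All cases of overdose must be reported immediately to the Sponsor".

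The dose is stated consistently elsewhere. Section 7.1.3.3: "A dose of 1200 mg atezolizumab will be administered by IV infusion every 3 weeks". The synopsis and Section 7.2 give the same figure. Section 5.3 explains it: "The fixed dose of 1200 mg (equivalent to an average body weight-based dose of 15 mg/kg) was selected". Section 7.1.3.1 describes a single-use vial at 60 mg/mL: "The vial is designed to deliver 20 mL (1200 mg) of atezolizumab solution but may contain more than the stated volume". Section 7.2.2 rules out any other dose level: "No reduction or modification of the atezolizumab dose will be allowed".

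The SAP contains no definition of overdose, so it neither repeats nor corrects the threshold.

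**The concern.** A threshold given as an amount and as a multiple should describe one quantity. Here the amount is lower than the dose that every patient in both arms is meant to receive, and the multiple points to a dose far above it. A site has no stated basis for choosing between them, and two sites acting in good faith could handle the same dosing error differently.

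The sentence is operative text, because it decides what must be reported to the sponsor at once whether or not the patient is harmed. The cross-reference makes this worse: Section 7.2 tells sites to record overdoses and incorrect administrations on the case report form, and then sends them to Section 9.4.1 for the detail.

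**Working it through.** **Inputs**

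- Stated threshold: 1000 mg, described as 5 times the dose (Protocol 9.4.1).
- Planned dose: 1200 mg per infusion (synopsis; 5.3; 7.1.3.3; 7.2).
- Vial: 20 mL at 60 mg/mL (7.1.3.1).
- Weight equivalence: 15 mg/kg on average (5.3).
- Other permitted atezolizumab doses: none (7.2.2).

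**Trying to reproduce the stated 1000 mg**

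1. Multiple × planned dose: 5 × 1200 = 6000 mg, not 1000 mg.
2. Via the vial: 20 mL × 60 mg/mL = 1200 mg, so five vials are again 6000 mg (100 mL).
3. Via body weight: 1200 / 15 = 80 kg, and 5 × 15 mg/kg × 80 kg = 6000 mg.
4. Backwards: 1000 / 5 = 200 mg, which is not given anywhere as an atezolizumab dose.

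No route gives 1000 mg.

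**Size of the conflict**

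- Stated threshold against one infusion: 1000 / 1200 = 0.83.
- Multiple against milligrams: 6000 / 1000 = 6.

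**What each half would classify as an overdose**

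| Dose given | By mg (≥ 1000 mg) | By multiple (≥ 6000 mg) |
|---|---|---|
| 1000 to below 1200 mg (incomplete infusion) | yes | no |
| 1200 mg (as planned) | yes | no |
| 2400 mg (second vial, 2 × 1200) | yes | no |
| 6000 mg (five vials) | yes | yes |

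The milligram reading counts correct and even incomplete infusions. The multiple leaves out everything above 1200 mg and below 6000 mg.

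**Other routes by which the sponsor would learn of an error**

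- Section 7.2: overdose or incorrect administration goes on the drug administration case report form, and related adverse events go on the adverse event form. No immediate-notice deadline is set there.
- Sections 9.4.5 and 9.4.6: serious adverse events are notified within 24 hours. This needs a serious event, not just a wrong dose.
- Section 9.4.8: a symptom-free overdose of the sponsor's product is a medical event of interest, reportable within 24 hours. It has no threshold of its own and may not cover atezolizumab.
- Section 16.2: giving a wrong dose is an example of an important deviation, and deviations are forwarded to the sponsor. No immediate deadline is given.

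What is left uncovered is mainly prompt notice of a non-serious atezolizumab error above 1200 mg and below 6000 mg, at a site that follows the multiple.

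**The case against.** The best defence is that the general definition protects the trial. It requires a dose that is excessive and of medical importance, and a planned 1200 mg infusion is neither. A reader might infer from the milligram figure that sites will report every infusion as an overdose; the documents do not support that. A site that follows the milligram figure would also report a 2400 mg error, so the gap opens only under the other reading. The remaining routes bring the information to the sponsor in any case, only less quickly. All of this stands, and it is why the point is minor. It does not make the threshold correct: it leaves each site to judge what the trial-specific sentence was meant to settle.

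A reader might also infer that 6000 mg would be the wrong threshold, or that a doubled dose is dangerous. The documents support neither. They do not show which half of the sentence is in error, and 5x is the only multiple the protocol states. At the implied 80 kg, 2400 mg is 2400 / 80 = 30 mg/kg, above the 20 mg/kg that is the highest dose described in Section 5.3. But that section also says no maximum tolerated dose was reached and no dose-limiting toxicity was seen, and the 80 kg is an average. Whether twice the dose should count as an overdose is a clinical decision for the sponsor.

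Nor do the documents support a threshold just above 1200 mg. They mention vial overfill but give no volume, and a small excess would fit poorly with the general definition.

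**Conclusion.** The inconsistency is real and is wrong as written. The milligram value is 0.83 times the planned dose and one sixth of the stated multiple, and nothing in the protocol or SAP reconciles the two. Severity is minor. The likely harm is slower notice to the sponsor of some non-serious dosing errors; efficacy, sample size, the dose-limiting toxicity rule and dosing are not affected.

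The arithmetic rests only on the fixed 1200 mg dose, which the documents state repeatedly. The view of practical harm assumes that sites apply the general definition sensibly and that the other reporting routes work as described. The Site Safety Manual and Pharmacy Manual are not among the documents and may contain overdose or dose-preparation instructions that narrow or widen the gap.

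**What to change.** In Section 9.4.1, replace the conflicting amount and multiple with one threshold that the sponsor confirms. It should lie above 1200 mg and be stated in mg with the matching multiple of 1200 mg. If five times the dose was intended, that is 6000 mg or more. Check the Site Safety Manual for the same figure.

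As an optional suggestion, the sponsor should consider a threshold no higher than 2400 mg (2 × 1200), so that a second-vial error triggers the immediate report. This is a preference for a more sensitive trigger, not a correction that the documents require.

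The cost is a one-line change in a protocol amendment, which under Section 16.1 needs FDA submission and IRB approval before use, plus the manual check. It can be included in the next routine amendment. The SAP needs no change.

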9.4.2 Adverse Event Severity

All AEs will be evaluated according to the NCI CTCAE v4.03 (2010).²⁹

For AEs not listed in this reference scale, severity will be assessed by the Investigator according to the criteria in Table 4.

Table 4 Adverse Event Severity Assessment

Grade 1 (Mild)	Mild; asymptomatic or mild symptoms; clinical or diagnostic observations only; intervention not indicated.
Grade 2 (Moderate)	Moderate; minimal, local or noninvasive intervention indicated; limiting age-appropriate instrumental activities of daily living (ADL)*.
Grade 3 (Severe)	Severe or medically significant but not immediately life-threatening; hospitalization or prolongation of hospitalization indicated; disabling; limiting self-care ADL**.
Grade 4 (Life threatening)	Life-threatening consequences; urgent intervention indicated.
Grade 5 (Death)	Death related to AE.

* Instrumental ADL refer to preparing meals, shopping for groceries or clothes, using the telephone, managing money, etc.

** Self-care ADL refer to bathing, dressing and undressing, feeding self, using the toilet, taking medications, and not bedridden.

Changes in the severity of an AE should be documented to enable an assessment of the duration of the event at each level of intensity. AEs characterized as intermittent require documentation of onset and duration of each episode.

9.4.3 Relationship to Investigational Drug

The Investigator will report his or her interpretation of the relationship between an AE and the study treatment on the basis of their clinical judgment and the definitions in [Table 5](#).

Table 5 Assessment of Relationship

Definitely related	AEs clearly attributable to study regimen administration.
Probably related	AEs for which there is a reasonable possibility of causal association to study regimen.
Possibly related	AEs for which there is confounding by comorbidities, medications or other considerations but for which it is not unreasonable that the AE may have been caused by study regimen. Note that it is not appropriate to invoke “you can’t rule it out.”
Not related	AEs that are considered clearly not causally related to study regimen, or for which there is a clear alternative explanation

AE = adverse event

If there is any question whether or not an AE is possibly, probably or definitely related, the Investigator should default to conservatism in categorization. Similarly, if an event meets one of the definitions described above and there is any doubt regarding the serious nature of an AE, the Investigator should default to conservatism by calling an AE an SAE.

9.4.4 Adverse Event Collection Period

AEs include any untoward signs (including abnormal laboratory findings) or symptoms experienced by the patient and will be collected from the time of enrollment until 30 days after the last dose of study drug. All enrolled patients will have periodic assessment of clinical and laboratory AEs. All AEs and SAEs will be collected at each Study Visit following completion of all scheduled procedures. Thereafter, new malignancies and SAEs that come to the attention of the site staff that are considered at least possibly related to CMB305 or atezolizumab will be collected until the last patient contact.

9.4.5 Adverse Event Reporting

At each study visit (including unscheduled visits), the Investigator, or designee, will determine whether any AEs have occurred. AEs will be reported in the patient’s medical record and on the AE CRF page and each will be classified according to the criteria in [Section 9.4.2](#) and [Section 9.4.3](#). If known, the diagnosis should be recorded, in preference to the listing of

individual signs and symptoms. Any pre-existing conditions that are detected as part of the initial screening procedures will need to be reported in the medical history and not as an AE. However, pre-existing conditions that worsen following enrollment should be reported as an AE.

AEs that occur during or within 24 hours after study drug administration should be captured as individual signs and symptoms on the AE eCRF rather than an overall diagnosis (e.g., record dyspnea and hypotension as separate events rather than a diagnosis of infusion-related reaction).

For all patients, progression of the cancer under study is not considered an AE unless it assessed by the Investigator as drug-related.

All AEs and SAEs that are unexpected and considered possibly, probably, or definitely related to study regimen will be reported to the US Food and Drug Administration (FDA) by IMDZ, or designee, in accordance with the requirements outlined in the Code of Federal Regulations (CFR), 21 CFR §312.32. Deaths due to cancer progression will not be reported as expedited events but must be reported to the Sponsor as SAEs within the 24 hour time period. The Investigator will continue to monitor the patient until any new, changed, or worsened AE resolves, returns to baseline, or until the Investigator and IMDZ agree that follow-up is no longer necessary. AEs must be followed until resolution whenever possible.

The Investigator is responsible for the appropriate medical care and safety of patients who have entered this study. The Investigator must notify the Sponsor within 24 hours if either of the following events occurs:

- Any event considered an MEOI (see [Section 9.4.8](#))
- Any event meeting the criteria for an SAE

The nature, severity, and frequency of AEs will be monitored on an ongoing basis for risk assessment and to determine if risk management interventions are warranted (i.e., expedited notification of safety findings to investigators, IRBs, or regulators; update of IB and ICF risks and re-consenting study patients; revision of safety monitoring procedures; revision of eligibility criteria or other study procedures).

9.4.6 Serious Adverse Event Reporting

If an SAE occurs, the Investigator must notify IMDZ within 24 hours of awareness of the event (see contact information below). If the SAE is fatal or life-threatening, IMDZ must be notified immediately, irrespective of the extent of available SAE information. In the rare event that the Investigator or designee does not become aware of the occurrence of a SAE immediately, the Investigator or designee must report the event within 24 hours of their awareness and document

the time of when his/her first awareness occurred. For all SAEs, the Investigator or designee is obligated to pursue and provide information to IMDZ in accordance with the timeframes for reporting specified above. In addition, the Investigator may be requested to obtain specific additional follow-up information in an expedited fashion. This information may be more detailed than that captured on the AE case report form. In general, this will include a description of the AE in sufficient detail to allow for a complete medical assessment of the case and independent determination of causality.

During the screening period, any new SAEs experienced by patients (pre-study treatment) will be reported to IMDZ if the events are considered related to study procedures. For the period after signing the ICF until Day 0, any new SAEs determined to be related to study tests or procedures (not including cancer-related events) and any hospitalizations that are experienced by patients will be reported on the SAE form and in the eCRF. From the start of study treatment (Day 0) until 30 days following cessation of study drug (or if the patient initiates new anticancer therapy, whichever is earlier), SAEs will be reported on the SAE form and in the eCRF. After that point, any SAE that comes to the attention of the site staff that may be causally related to study drug (i.e., there is a reasonable possibility that the event may have been caused by the drug) will be reported to IMDZ.

SAEs will be monitored until they have resolved, returned to baseline, or until they are no longer clinically significant, stable, or do not require additional follow-up, as judged by the Investigator and IMDZ.

STUDY CONTACT FOR REPORTING SERIOUS ADVERSE EVENTS	
Everest Clinical Research Inc.	
Telephone:	PPD [redacted] (office) or PPD [redacted] (mobile)
Fax:	See the SAE Report Completion Guidelines
Email:	SAE forms to PPD [redacted] Supplemental information to PPD [redacted]

